8.3 TIME PERIOD AND FREQUENCY FOR EVENT ASSESSMENT

The occurrence of an AE or SAE may come to the attention of study personnel during a clinic visit with the provider or the nurse counselor during the intervention period or telephone surveys at 3 months). All AEs, including local and systemic reactions not meeting the criteria for SAEs, will be captured on the appropriate reporting form. Information to be collected includes event description, time of onset, participants' self-assessment of severity, relationship to study product, and time of

resolution/stabilization of the event. All AEs occurring while in the study will be documented appropriately regardless of relationship. All AEs will be followed to adequate resolution.

Any medical condition that is present at the time that the participant is screened will be considered as baseline and not reported as an AE. However, if the study participant's condition deteriorates at any time during the study, it will be recorded as an AE. UPs will be recorded in the data collection system throughout the study.

Changes in the severity of an AE will be documented to allow an assessment of the duration of the event at each level of severity to be performed. AEs characterized as intermittent require documentation of onset and duration of each episode.

The PI will record all reportable events with start dates occurring any time after informed consent is obtained until 7 (for non-serious AEs) or 30 days (for SAEs) after the last day of study participation. At each study visit, the investigator will inquire about the occurrence of AE/SAEs since the last visit. Events will be followed for outcome information until resolution or stabilization. All unresolved adverse events will be followed by the investigator until the events are resolved, the subject is lost to follow-up, or the adverse event is otherwise explained. At the last scheduled visit, the investigator will instruct each subject to report any subsequent event(s) that the subject, or the subject's personal physician, believes might reasonably be related to participation in this study. The investigator will notify the study sponsor of any death or adverse event occurring at any time after a subject has discontinued or terminated study participation that may reasonably be related to this study.

8.4 REPORTING PROCEDURES-NOTIFYING THE IRB AND SPONSOR

8.4.1 Adverse Event Reporting Adverse events will be communicated to the School of Medicine (SoM) and ISMS IRB at the time of continuing review in summary or aggregate form, to the DSMB in aggregate form at each scheduled meeting, and to the Program Officer at NIH in aggregate/summary form in the annual Progress Report. Non-harmful/Expectable events are not recorded or reported to the IRB.

8.4.2 Serious Adverse Event Reporting (1) Report event to IRB within 24 hours using the SoM Report form, (2) Report event to NIH Program Officer and DSMB within 24 hours, (3) Report additional details of event and actions taken to IRB, DSMB, and NIDA Program officer within 72 hours, (4) Communicate DSMB findings to IRB and NIH, (5) Respond to requests for additional information by and/or recommendations from the IRB, DSMB and NIDA.

8.4.3. Unanticipated Problem (UP) Reporting Incidents or events that meet the OHRP criteria for UPs require the creation and completion of an UP-report form. It is the site investigator's responsibility to report UPs to their IRB and to the study sponsor. The UP report will include the following information:

- Protocol identifying information: protocol title and number, PI's name, and the IRB project number;
- A detailed description of the event, incident, experience, or outcome;
- An explanation of the basis for determining that the event, incident, experience, or outcome represents an UP;
- A description of any changes to the protocol or other corrective actions that have been taken or are proposed in response to the UP.

To satisfy the requirement for prompt reporting, UPs will be reported using the following timeline:

- UPs that are SAEs will be reported to the IRB and to DSMB and study sponsor within 24 hours of the investigator becoming aware of the event.

- Any other UP will be reported to the IRB and to DSMB and sponsor within one week of the investigator becoming aware of the problem.
- All UPs will be reported to appropriate institutional officials (as required by an institution's written reporting procedures), the supporting agency head (or designee), and OHRP within 72 hours of the IR's receipt of the report of the problem from the investigator.

8.4.4. Reporting Pregnancy. Pregnant women are excluded from the study because of questions about the safety of NRT during pregnancy.

8.5 REPORTING PROCEDURES NOTIFYING THE STUDY SPONSOR (see section 8.4).

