8. ASSESSMENT OF SAFETY

8.1 SPECIFICATION OF SAFETY PARAMETERS. This is a minimal risk study. Patients enrolled in the RCT will receive a standard care behavioral intervention from their health care providers (brief counseling plus Quitline counseling) vs provider brief counseling plus the addition of 6 sessions of nurse delivered counseling vs brief physician counseling + multisession nurse delivered counseling +NRT. Eligibility for NRT will be assessed at the time study eligibility is assessed and prior to enrollment. It is important to note that the nicotine gum is an over-the-counter medication, proven safe, with minimal potential side effects. In addition, there are no significant interactions between NRT and HIV treatments (<http://www.hivdruginteractions>). Patients with a recent history of MI (four weeks), uncontrolled hypertension, arrhythmia, or worsening angina pectoris will not be eligible to enroll. Potential side effects related to NRT will be assessed by the nurse counselor at each counseling visit and reported in the tracking form that counselors use to document visits. The length of treatment with NRT (6 weeks) will generally coincide with those visits. At the time of enrollment participants in the nicotine gum arm will be told of the common side effects (e.g., Rash, mouth, tooth, or jaw problems, palpitations) they may experience and asked to report any problems to the nurse and/or doctor in the clinic or to call the contact number on the consent form. They will also be told how to reduce the likelihood of common side effects, including not smoking while using the gum. Counselor training will include information about potential side effects and to explore potential reasons for side effects and suggest ways to reduce side effects. The PIs will be contacted within 24 hours if the physician or counselor believes there is an AE or SAE, otherwise, forms will also be reviewed by the ISMS and NYU PIs weekly to assess the need to reduce the dose or discontinue the medication.

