8.1.1. Definition of Adverse Events

An adverse event (AE) is any symptom, sign, illness or experience that develops or worsens in severity during the course of the study. Intercurrent illnesses or injuries should be regarded as adverse events. Abnormal results of diagnostic procedures are considered to be adverse events if the abnormality:

- results in study withdrawal
- is associated with a serious adverse event
- is associated with clinical signs or symptoms
- leads to additional treatment or to further diagnostic tests
- is considered by the investigator to be of clinical significance

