8.2. CLASSIFICATION OF AN ADVERSE EVENT

8.2.1. Severity of Event

For AEs not included in the protocol defined grading system, the following guidelines will be used to describe severity.

- **Mild** – Events require minimal or no treatment and do not interfere with the participant's daily activities.
- **Moderate** – Events result in a low level of inconvenience or concern with the therapeutic measures. Moderate events may cause some interference with functioning.
- **Severe** – Events interrupt a participant's usual daily activity and may require systemic drug therapy or other treatment. Severe events are usually potentially life-threatening or incapacitating.

8.2.2. Relationship to the study agent. The PIs will assess if the AE is related or not related to the NRT.

- **Related** – The AE is known to occur with the study agent, there is a reasonable possibility that the study agent caused the AE, or there is a temporal relationship between the study agent and event. Reasonable possibility means that there is evidence to suggest a causal relationship between the study agent and the AE.
- **Not Related** – There is not a reasonable possibility that the administration of the study agent caused the event, there is no temporal relationship between the study agent and event onset, or an alternate etiology has been established.

8.2.3. Expectedness. [name] and [name] will be responsible for determining whether an AE is expected or unexpected. An AE will be considered unexpected if the nature, severity, or frequency of the event is not consistent with the risk information previously described for the study agent.

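### Section 8.4.1 exempts non-harmful or expectable events from being recorded, which conflicts with 8.1 and 8.3 and could understate adverse event frequencies in the nicotine gum arm

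*Combined protocol and SAP*

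**What the plan says.** The combined protocol and SAP deals with the recording of adverse events (AEs) in several places.

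- **8.1.1 (definition).** "An adverse event (AE) is any symptom, sign, illness or experience that develops or worsens in severity during the course of the study". Mild or expected events are not carved out.
- **8.3 (capture).** "All AEs, including local and systemic reactions not meeting the criteria for SAEs, will be captured on the appropriate reporting form", and "All AEs occurring while in the study will be documented appropriately regardless of relationship". Again there is no exception for expectedness.
- **8.1 (gum side effects).** "Potential side effects related to NRT will be assessed by the nurse counselor at each counseling visit and reported in the tracking form". The investigators review forms weekly. The examples given to Arm 3 participants are "e.g., Rash, mouth, tooth, or jaw problems, palpitations".
- **8.2.3 (expectedness).** "An AE will be considered unexpected if the nature, severity, or frequency of the event is not consistent with the risk information previously described".
- **8.4.1 (reporting).** AEs go in summary or aggregate form to the two IRBs at continuing review, to the DSMB at each scheduled meeting, and to NIH in the annual progress report. The paragraph then ends: "Non-harmful/Expectable events are not recorded or reported to the IRB".

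**The concern.** Sections 8.3 and 8.4.1 are both current text, and site staff cannot follow both as written. One has every AE captured. The other, on its plain wording, leaves a class of events unrecorded.

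That class plausibly contains the gum's known effects. Only Arm 3 receives gum, so any loss would fall on one arm. The DSMB is asked in 8.8 to assess safety data on each arm, and what it receives under 8.4.1 is an aggregate. If expectable events never enter the AE data, that aggregate is too low for the arm in which they are most likely.

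The protocol's own safety triggers also depend on the count. Section 8.2.3 and the definition of an unanticipated problem in 8.1.3 both treat an unusual frequency as a reason to call an event unexpected. Frequency is hard to judge for events that are not recorded.

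**Working it through.** The plan gives no figure on this point, so the check is a comparison of the texts.

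1. **Is there a conflict?** Section 8.3 captures all AEs, including reactions that are not serious, whatever their relationship to treatment. The definition in 8.1.1 is equally broad. A mild sore jaw from chewing gum is an AE under 8.1.1 and must go on a form under 8.3. Under 8.4.1, if it counts as non-harmful or expectable, it is not recorded. Section 8.1 requires the same symptom to be noted on the tracking form, so it too disagrees with 8.4.1.

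2. **Which events are affected?** The 8.4.1 label joins two words with a slash and defines neither. Section 8.2.3 defines only when an AE is unexpected. By that test, effects the protocol already describes are not unexpected unless their nature, severity or frequency departs from the description. Those effects are the ones listed in 8.1, plus the palpitations, nausea and light-headedness in 6.1.5. If the slash means either, all of them fall in the exempt class. If it means both, an event must also be non-harmful, and one that leads to a change in gum use may not qualify.

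3. **Who is exposed?** Section 4.1 gives gum to Arm 3 only. The arm size is 13 sites × 16 per arm = 208, or 672 ÷ 3 = 224, depending on which stated figure is used. The documents give no rate for any gum side effect, so no number of lost events can be derived.

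4. **Is there another route into the safety data?** The tracking form is one. As 8.1 describes it, the investigators' weekly review of forms serves to decide whether a dose should be reduced or stopped. That is a review of individual patients, not a count by arm. No section says that the form feeds the AE dataset or the DSMB, IRB or NIH aggregates. Section 6.1.6 also describes a counselors' tracking form and lists only questions about gum use; the documents do not say whether this is the same form.

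5. **Does other wording settle the meaning?** It does not. Section 8.3 also says that the PI records events that are reportable. Read together with 8.4.1, that could suggest that an event not reportable to the IRB need not be recorded.

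**The case against.** The strongest defence is that the sentence concerns the IRB only. It sits under a heading about notifying the IRB and sponsor, it ends by naming the IRB, and capture is governed by 8.3. Section 8.2.3 supports this reading, because judging an event on its frequency presupposes that it was recorded. The reading may well be what was intended, but nothing in the documents confirms it, and the words on recording would then add little. Nor does it clear the paragraph completely. The opening sentence sends AEs to the IRBs in aggregate, and the last sentence withholds some of them without saying whether the aggregate is included.

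The second defence is the tracking form. It stands in part: gum side effects would not vanish from all study records, and the investigators would see them. The DSMB charter mentioned in 8.8 is meant to define each data element and might close the gap, but it is not among the documents.

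A reader might infer three stronger things that the text does not support.

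- **Arm 3 will show almost no gum-related events whatever the true rate.** That would need sites to apply 8.4.1 literally, set 8.3 aside, and never move tracking form entries into the AE data.
- **A rise in frequency could not be detected.** The assessment at each counseling visit and the weekly review give it a route, although not one designed for counting.
- **The sponsor chose to leave gum effects unrecorded.** Sections 8.1 and 8.3 point the other way. This looks like loose drafting.

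**Conclusion.** The inconsistency among 8.1, 8.3 and 8.4.1 is real and should be corrected. As worded, 8.4.1 permits a site to leave expectable gum effects out of the AE record. If sites do so, and tracking form entries are not transferred, AE frequencies in Arm 3 would be understated in the aggregates and the frequency criterion in 8.2.3 would be weakened.

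The effect could range from nothing, if sites follow 8.3 and read 8.4.1 as a rule about the IRB, to a material undercount of mild, known effects in one arm. The documents do not allow a figure between these. Serious AEs have their own reporting rule in 8.4.2. Section 9.1 plans no formal comparison of AEs, so what is at stake is the descriptive safety review by the DSMB and the reports to the IRBs and NIH. The primary efficacy result is not affected.

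**What to change.** Reconcile 8.1, 8.3 and 8.4.1 so that recording and IRB reporting are stated separately:

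- In 8.4.1, delete the words that exempt events from being recorded.
- State that all AEs, expectable or not, are recorded in the study AE data, including those noted on the counselors' tracking form, and are included in the aggregate DSMB summaries by arm.
- State that the 8.4.1 exemption concerns reporting to the IRB only. Say whether it covers individual reports alone or also the continuing-review aggregate, so that it agrees with the sentence before it. Which of the two applies is for the sponsor and the IRBs; resolving the conflict does not require expectable events to be added to the IRB aggregate.
- Define the exempt class, and say whether an event must be both non-harmful and expectable or only one of these.

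The cost is a few sentences in an amendment and a step that carries side effects from the tracking form to the AE form. Sections 8.1 and 8.3 already require both kinds of record, so no new data are collected from patients. For patients already treated, completed tracking forms can be compared with the AE records to see whether any events were left out.

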8.6. REPORTING PROCEDURES – NOTIFYING THE FDA (NA)

8.7. HALTING RULES. (NA) This is a minimal risk study. Only those participants randomized to receive the over the counter drug, nicotine gum, will be receiving medication. If patients who are receiving NRT experience side effects these will be addressed as described above. If they must discontinue the nicotine gum they can still choose to continue to participate in the counseling component of the intervention.

8.8. SAFETY OVERSIGHT. It will be the responsibility of the PIs to oversee the safety of the study. This safety monitoring will include careful assessment and appropriate reporting of AEs and SAEs as noted above, as well as the construction and implementation of a site data and safety-monitoring plan. Safety oversight will be under the direction of a DSMB composed of individuals with the appropriate expertise, including a tobacco use treatment expert, an HIV expert and a biostatistician. The DSMB will meet at least semiannually to assess safety and efficacy data on each arm of the study. The DSMB will operate under the rules of an approved charter that will be written and reviewed at the organizational meeting of the DSMB. Each data element that the DSMB needs to assess will be clearly defined. The DSMB will provide its input to Drs. [name] and [name]. The primary responsibilities of the DSMB are to 1) periodically review and evaluate the accumulated study data for participant safety, study conduct and progress, and, when appropriate, efficacy, and 2) make recommendations concerning the continuation, modification, or termination of the trial. The DSMB will consider study-specific data as well as relevant background knowledge about the intervention, or patient population under study.

9.0 STATISTICAL CONSIDERATIONS

9.1 STATISTICAL AND ANALYTIC PLANS AND METHODS (SAP)

AIM 1: To explore barriers to tobacco cessation among HIV+ smokers.

Survey data will be summarized using descriptive statistics. Qualitative data from the audio recordings of the KIs will be transcribed verbatim in Vietnamese by ISMS, translated into English and back translated. Two trained NYU and ISMS coders will analyze the interview data using a priori concepts that emerge from the quantitative data and both an inductive and deductive approach (open coding and coding of theoretical constructs). We will use Atlas ti. to facilitate our multi-step iterative coding and analyses. Data coding will begin with independent reading of the transcripts to identify preliminary themes and relevant patterns, followed by focused coding to identify clustered concepts and to organize ideas, and finally identification of major themes.

Throughout, coders will meet to review their coding, conduct team debriefing meetings, and reach consensus on code names and meanings. Once all transcripts have been collaboratively coded, analytic domains will be identified and major and minor thematic areas described.

AIM 2: (Primary effectiveness endpoint analysis) To compare the effectiveness of three interventions to increase tobacco cessation among PLHW who smoke. The primary analytic approach used to compare study arms is conditional logistic regression.^{17,18} This fixed effects approach was chosen as primary because of the modest number of sites and the fact that they are not very heterogeneous. Because some methodologists have advocated mixed effects models even when the number of sites is small,^{19,20} we will use a multilevel logistic regression model as an alternative, sensitivity analysis approach. In an intent-to-treat analysis of all study entrants,

conditional logistic regression analysis will compare study arms on the primary outcome, 7-day point prevalence CO confirmed (<10 ppm) tobacco abstinence captured at 6-months follow up. The outcome will be regressed on indicator variables for study arm and OPC site will be the stratification variable. Pairwise comparisons of arms will be undertaken to determine which arms are significantly different. Pairwise comparisons will be adjusted for multiple comparisons using the Tukey method.²¹ Effect magnitudes will be based on odds ratios for the pairwise comparisons, which will be calculated by exponentiating the coefficients for pairwise contrasts. Secondary cessation outcomes, HIV-related outcomes, and hypothesized mediators (e.g., risk perceptions, self-efficacy) also will be analyzed with conditional logistic regression, or a different fixed effects regression appropriate to the type of outcome variable. Multilevel regression will be used as sensitivity analysis. To calculate indirect effects of study arm on abstinence via potential mediators, the Mplus statistical modeling software will be used with bootstrapping of products of direct effects.^{22,23} Patient characteristics (e.g., sex, substance use, health) will be included as covariates in all analysis and explored as potential effect modifiers. To examine effects of fidelity or “dose” of intervention, we will estimate effects of receiving the full dose of each intervention component, or not, using *complier average causal effect* estimation.^{24,25} Using patient characteristics associated with receiving a full dose among those offered each component, the Complier Average Casual Effect (CACE) approach finds similar patients not offered the component but likely to receive a full dose if they had been offered. This permits patients who receive the full dose of specific components to be compared with similar patients not offered the component, in order to estimate intervention effects for “compliers” only. Identifying the intervention’s impact on compliers deepens our understanding of to whom the results apply, and to whom they do not, thereby suggesting possible adaptations of components with less than perfect fidelity or uptake. CACE is a type of per protocol analysis, with similarities to other approaches for estimating causal effects with noncompliance or partial dose, which constitutes a shift from estimating effects of treatment *offered* to treatment *received*.

AIM 3: Given the small sample size of provider surveys, we will use descriptive statistics to summarize the quantitative data and assess changes pre and post-trial in provider and clinic-level factors. We will use bivariate analysis to explore differences by study site and to assess relationships between provider and perceived intervention characteristics (Table 3) and adherence (fidelity) to standard care (i.e., Ask, Advise, Assist, Refer) based on their self-report (survey Appendix). Qualitative data from providers and program directors will be transcribed, translated, and back translated. [name] fluency in English and Vietnamese will ensure “conceptual equivalence.” Two trained NYU and ISMS coders will analyze the interview data using a priori concepts that emerge from the quantitative data and both an inductive and deductive approach (open coding and coding of theoretical constructs).^{26,27} We will use Atlas ti. to facilitate our multi-step iterative coding and analyses. Data coding will begin with independent reading of the transcripts to identify preliminary themes and relevant patterns, followed by focused coding to identify clustered concepts and to organize ideas, and finally identification of major themes. Throughout, coders will meet to review their coding, conduct team debriefing meetings, and reach consensus on code names and meanings. Once all transcripts have been collaboratively coded, analytic domains will be identified and major and minor thematic areas described. Our analysis will also integrate the data to examine how qualitative themes converge with or expand on quantitative findings. This will include creating a table that examines key constructs from our frameworks with responses from all sources of data. We will then triangulate findings from pre and post assessments by developing a thematic matrix that includes system, clinic and provider-level characteristics, and compare side by side, those factors that were identified as facilitating or hindering the implementation process. Findings will be used to create a heuristic model to inform further optimization of the implementation process, and sustainability, if found

effective. Data will be shared with the SAC during meetings to inform discussions about strategies for facilitating sustainability and dissemination.

AIM 4: When comparing smokers and non-smokers at baseline on the HFIAS, power is 80% to detect a standardized mean difference of $d=0.46$ (about half a standard deviation, a difference of 3 HFIAS points assuming a standard deviation of 6) given the proposed sample size of $n= 150$ (75 smokers and 75 non-smokers). When estimating the relation between income and HFIAS, power is 80% to detect a squared multiple correlation of $R^2=.05$ given the proposed sample size of $n=150$. When estimating the impact of smoking cessation on HFIAS at the 6-month follow-up, power is 80% to detect a standardized mean difference of $d=0.89$ (about nine tenths of a standard deviation, a difference of 6 HFIAS points) given the proposed sample size of $n=75$ smokers at baseline and assuming at least 16% of smokers ($n=12$) achieve cessation.

9.2 STATISTICAL HYPOTHESIS. The primary hypothesis is that more intensive counseling delivered by a trained nurse (ARM 2) will be more effective than provider brief counseling plus Quitline counseling (ARM 1) in increasing smoking abstinence. We further hypothesize that adding nicotine replacement therapy to the more intensive counseling will increase cessation rates more than the intensive counseling alone (ARM 3).

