5.2 EXCLUSION CRITERIA

5.2.1. Patient Exclusion Criteria The few individuals for whom there is a need for precaution in using NRT will be excluded

- recent myocardial infarction (2 weeks)
- serious underlying arrhythmias
- patients who are pregnant or nursing
- any patient who participated in the study during wave 1 at OPC site 1-5 and then transferred to OPC site 6-13 during wave 2

We will also exclude those who are unable to demonstrate capacity for consent and patients already enrolled in a tobacco use treatment program.

Our pilot data indicate that about half of tobacco users in these sites are dual users (cigarettes and waterpipe); only about 12% use waterpipe alone. VQUIT found that dual users who received VHW counseling had 6-month CO confirmed quit rates that were comparable to patients who used cigarettes only. Therefore, we will not exclude dual users. We will exclude waterpipe only users because the intervention is based on effectiveness data for dual and cigarette users and there is a lack of evidence for efficacy or effectiveness of NRT use in this population.

5.2.2. Employee exclusion criteria. Employees who are unwilling to sign consent will be excluded.

5.3 VULNERABLE SUBJECTS. Employees are considered a vulnerable population. Research staff who work for the research institute (ISMS) will be responsible for consenting employees. Research staff are trained to emphasize that participation is voluntary and employees' decision will not affect their job evaluation, promotions and work-related assignments.

5.4 STRATEGIES FOR RECRUITMENT.

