9.3 PLANNED INTERIM ANALYSIS

We will conduct descriptive statistics to be presented to the DSMB at the biannual meetings. This will include analysis of recruitment progress to address any barriers and to review the safety data.

10. SOURCE DOCUMENTS AND ACCESS TO SOURCE DATA/DOCUMENTS. The study case report form (CRF) is the primary data collection instrument for the study. All data requested on the CRF must be recorded. All missing data must be explained. If a space on the CRF is left blank because the procedure was not done or the question was not asked, write "N/D". If the item is not applicable to the individual case, write "N/A". All entries should be printed legibly in black ink. If any entry error has been made, to correct such an error, draw a single straight line through the incorrect entry and enter the correct data above it. All such changes must be initialed and dated. For clarification of illegible or uncertain entries, print the clarification above the item, then initial and date it. Access to study records will be limited to IRB-approved members of the study team. The investigator will permit study-related monitoring, audits, and inspections by the IRB, the sponsor, government regulatory bodies, and University compliance and quality assurance groups of all study related documents (e.g. source documents, regulatory documents, data collection instruments, study data etc.). The investigator will ensure the capability for inspections of applicable study-related facilities. Participation as an investigator in this study implies acceptance of potential inspection by government regulatory authorities and applicable University compliance and quality assurance offices.

11. QUALITY ASSURANCE AND QUALITY CONTROL (QC).

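### Optional, low-cost improvement: state which Tukey procedure is meant. With three arms, a closed step-down version keeps family-wise error at 0.05, loses no rejection and can help the two adjacent contrasts

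*Combined protocol and SAP*

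**What the plan says.** The Aim 2 analysis in Section 9.1 fits a conditional logistic regression with site as stratum. It then states: "Pairwise comparisons of arms will be undertaken to determine which arms are significantly different". The next sentence reads: "Pairwise comparisons will be adjusted for multiple comparisons using the Tukey method". On estimation: "Effect magnitudes will be based on odds ratios for the pairwise comparisons". The Statistical Analysis entry of the Protocol Summary repeats all three statements.

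Section 9.2 names two directional hypotheses, both about adjacent arms. The first: "The primary hypothesis is that more intensive counseling delivered by a trained nurse (ARM 2) will be more effective than provider brief counseling" (plus Quitline counselling). The second: "We further hypothesize that adding nicotine replacement therapy to the more intensive counseling will increase cessation rates more than the intensive counseling alone". Arm 3 v Arm 1 is not named there, but it belongs to the family of pairwise comparisons in Section 9.1.

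The Aim 2 text gives no alpha, no sidedness, no quit rate by arm and no power. It does not say whether Tukey is applied in one step or stepwise.

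**The concern.** Single-step Tukey holds every pair to the critical value that suits the largest of three comparisons. If counselling and nicotine gum each add something, the adjacent differences are smaller than Arm 3 v Arm 1. The two hypothesised contrasts then lose most under a uniform threshold.

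With three arms that price need not be paid in full. Once the hypothesis that all three arms are equal is false, at most one pair can be truly equal. Single-step Tukey then spends only about 1.8% on that pair, although 5% is allowed. The unspent error could go to the contrasts the trial was set up to answer. Because the version is not stated, the primary decision rule is also left partly open.

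**Working it through.** **Inputs from the documents.** There are three arms with equal allocation. The stated 672 patients give 672/3 = 224 per arm; 13 sites × 16 per arm give 208 per arm. Both were used, and the choice does not affect the conclusion.

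**Assumptions.** Two-sided family-wise 0.05; single-step Tukey as the comparator; all quit rates (Arm 1/Arm 2/Arm 3); no dropout. The plan states no power for Aim 2, so there is no figure to reproduce.

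**Step 1, critical value.** q(0.95; 3 groups, infinite df)/√2 = 2.344, a two-sided per-pair p of 0.0191. An unadjusted 0.05 test needs 1.960.

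**Step 2, the closed rule.** Any two true pairwise nulls imply that all three arms are equal. The closed family is therefore the global null plus three single pairs. Test the global null by max|z| > 2.344. If it is rejected, test each pair at |z| > 1.960; otherwise declare none.
- *Error control:* if all arms are equal, an error needs max|z| > 2.344, with probability 0.05. If exactly one pair is equal, an error needs that pair to pass a 0.05 test.
- *Nothing lost:* a pair with |z| > 2.344 opens the first step and also exceeds 1.960.
- *Any-pair power unchanged:* both rules reject at least one pair exactly when max|z| > 2.344.
- *First step must be the range test:* with three equally spaced arms and |z| = 2.344 for the extremes, the 2-df chi-square is 2.344² = 5.49, below 5.99. A chi-square first step would lose a Tukey rejection.

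**Step 3, size of the gain.** Simulation with 400,000 trials per scenario, unstratified Wald tests of log odds ratios. At 10/18/26%:

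| Per arm | Arm 2 v 1 | Arm 3 v 2 | Both adjacent |
|---|---|---|---|
| 208 | 49.2% → 65.1% | 35.0% → 50.4% | 9.5% → 25% |
| 224 | 53.6% → 68.3% | 37.9% → 53.1% | 12% → 29% |

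Arm 3 v 1 gains about 0.2 points. At 208 per arm the chance of at least one significant pair is 97.9% under both rules.

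Gains in points at other assumed rates:

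| Rates | Arm 2 v 1 | Arm 3 v 2 |
|---|---|---|
| 16/26/36% | 14–15 | 15–16 |
| 10/20/30% | 11–13 | 15–16 |
| 10/15/20% | 11 | 10 |
| 10/13/16% | 4 | 4 |
| 16/18/20% | 1.4–1.5 | 1.3–1.4 |
| 10/30/50% | 0.1 | 1.4–2.0 |

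These are illustrations, not bounds; 3/9/15% gives up to 17.6. Where gum adds nothing, Arm 3 v 1 gains as much as Arm 2 v 1 (about 7.5 points each at 10/18/18%).

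**Step 4, under the planned model.** Exact conditional logistic likelihood, 13 strata, 16 per arm per site, one covariate (assumed log odds ratio 0.5 per SD), assumed site SD 0.3 on the logit. At 10/18/26%, Arm 2 v 1 goes from 51.5% to 66.6% and Arm 3 v 2 from 34.3% to 48.9%. At 16/18/20% the gains are 1.2 and 1.3 points.

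**Step 5, error rates.** Step-down family-wise error was 0.036–0.049 over complete and partial nulls with the Wald tests, and 0.043 under no effect with the conditional model. At 10/20/20%, wrongly declaring Arm 3 different from Arm 2 rises from 1.8% to 4.8–4.9% (conditional model: 1.9% to 5.0%). Control is asymptotic: an extreme case (10/50/50%, 224 per arm) gave 5.2%. Tukey's own rate there was also above nominal (2.0% against 1.9%), so the excess comes from the Wald approximation. No Tukey rejection was lost in any scenario.

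**The case against.** The strongest reply is that nothing is broken: the plan prespecifies a recognised method that controls family-wise error over all pairs. That stands. A reader might infer that the adjustment is wrong, or that the trial forfeits 15 points of power. The documents support neither. The method is valid, the 15 points belong to the adjacent contrasts at one assumed set of rates, and any-pair power is identical under both rules.

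The premise is also an assumption, since the text never says single-step. If step-down was meant, there is no gain. What the documents firmly show is narrower: alpha, sidedness and version are missing.

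There is a good reason to keep single-step Tukey. The plan reports pairwise odds ratios, and single-step decisions agree with Tukey simultaneous intervals. Under step-down, every added rejection has a Tukey interval that includes 1. At least one occurs in about 28% of trials at 10/18/26%, and in about 4% at 16/18/20%. Conversely, an unadjusted interval can exclude 1 for a pair not declared significant, in about 7% of trials with no effect and 17–18% at 10/13/16%. These are real costs.

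Step-down is not the only alternative. Testing Arm 2 v 1 and then Arm 3 v 2 in fixed sequence at 0.05 gives 82.2% on the first, against 76.7% for step-down, at 10/20/20% with 208 per arm. At 10/18/26% the chance of both is the same (25.3%). But a fixed sequence has lower power for Arm 3 v 2 taken alone and can lose rejections that Tukey makes.

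Finally, a late change may be hard to defend. The trial is unblinded. Section 5.2.1 excludes "any patient who participated in the study during wave 1 at OPC site 1-5" who then transferred to a wave 2 site, and the version log dates that addition to December 2022, so wave 1 outcomes may already exist. Section 8.8 says: "The DSMB will meet at least semiannually to assess safety and efficacy data on each arm of the study". Section 9.3 promises only descriptive statistics, and says of them: "This will include analysis of recruitment progress to address any barriers and to review the safety data". These passages do not show that anyone responsible for the analysis plan has seen outcomes by arm, but they make the opposite harder to document.

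**Conclusion.** An optional improvement, not an error. Given single-step Tukey at two-sided family-wise 0.05, the step-down rule dominates it on rejections at the same large-sample family-wise level. The dominance follows from logic; its size does not. Across the assumed rates shown, the gain on an adjacent contrast runs from 0.1 to about 16 points. It is small when effects are tiny or when Tukey power is already near 100%. The price is looser agreement between decisions and intervals, and an error rate on a single remaining true null that rises from about 1.8% to about 5%, still within the family-wise level. Whether this trial would benefit cannot be settled, because the plan gives no arm-level quit rates.

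**What to change.** In Section 9.1 and in the Statistical Analysis entry of the Protocol Summary, state:

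- Family-wise alpha is 0.05, two-sided. If the largest absolute pairwise z exceeds the Tukey critical value for three arms, each pair is tested at two-sided 0.05; otherwise no pair is declared significant.
- Significance is judged only by the step-down adjusted p-value: the larger of the pair's unadjusted p-value and the Tukey p-value of the largest absolute z.
- Odds ratios carry Tukey simultaneous 95% intervals. Unadjusted 95% intervals may be added, labelled descriptive.

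Make this a dated amendment that documents that those making it have not seen outcomes by arm. If that cannot be shown, keep single-step Tukey and state its alpha, sidedness and version. If step-down was already intended, only say so.

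The cost is matching text in two places, with no new patients or data. The text should also disclose the two downsides: the interval mismatch and the higher error on a single true null.
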